1.1 Description

PROTOCOL TITLE: A phase II trial to improve outcomes in patients with resected pancreatic adenocarcinoma at high risk for recurrence using epigenetic therapy

DATE PROTOCOL FINAL:	
INDICATION:	Cancer Therapy
STUDY PHASE:	Phase II

BACKGROUND AND RATIONALE:

DNA methylation is often abnormal in cancer cells and can lead to the inactivation of tumor suppressor genes. Hypomethylating agents, such as 5-azacitidine, have been shown to reverse DNA hypermethylation and allow for reactivation of tumor suppressor genes and ultimately lead to cancer cell death. These agents are currently the standard of care in myelodysplasia and have also shown some efficacy in early phase trials for solid tumors. In pancreatic cancer cell lines, promoter regions of several tumor suppressor genes have been demonstrated to be abnormally hypermethylated. The addition of hypomethylating agents has restored the expression of these genes and has decreased tumor growth. While most of the trials have used the subcutaneous delivery of azacitidine, the oral formulation, CC-486, is currently being studied in a phase I trial for MDS/AML and has been shown to be bioavailable, well-tolerated, and produce similar clinical responses as the subcutaneous version.

Pancreatic adenocarcinoma is a very deadly disease, with only 20% of patients being candidates for possible curative surgery at presentation. However, the majority of these patients will recur. Patients that are node positive or margin positive at the time of resection have a greater than 90% chance of recurrence and death from disease. After surgery and adjuvant therapy, patients are monitored with CT scans and CA 19-9 levels. In some patients, CA 19-9 levels rise before visible disease progression, suggesting micro-metastatic disease. After completing adjuvant chemotherapy, further chemotherapy is typically not used before recurrent disease is visible even with an elevated biomarker; however a therapy that is well-tolerated would be ideal in this setting. The goal of this trial is to demonstrate that CC-486 is well tolerated and effective when given after adjuvant therapy in patients with high risk disease (rising CA 19-9, node positive disease, or margin positive disease) by prolonging time to visible disease recurrence, increasing response rates to eventual chemotherapy, and increasing overall survival.

STUDY OBJECTIVES:

Primary objective:

To improve progression free survival in high risk patients with resected pancreatic adenocarcinoma who have node positive disease, margin positive disease, and/or elevation in CA 19-9 treated with CC-486 as compared to observation after completion of adjuvant therapy.

Secondary objectives:

- 1) To improve response rates to first-line chemotherapy (partial and complete response) after recurrence in patients treated with CC-486 after completing adjuvant therapy.
- 2) To improve overall survival in patients with resected pancreatic adenocarcinoma treated with CC-486.
- To evaluate resected pancreatic cancer tissue and biopsies at time of recurrence for epigenetic and genetic alterations to determine the pharmacodynamic effects of CC-486.
- 4) To evaluate resected pancreatic cancer tissue and blood samples to identify predictive signatures of possible recurrence and the benefit of hypomethylating therapy.
- 5) To evaluate quality of life during CC-486 using the FACIT-Hep questionnaire

STUDY ENDPOINTS:

Primary endpoint:

The primary endpoint of the trial is to demonstrate an increase in the progression free survival, PFS, in resected pancreatic cancer patients treated with CC-486.

Secondary endpoints:

- Response rate (including partial and complete response) to first-line chemotherapy when given after visible disease recurrence in patients primed with CC-486 compared to observation.
- 2) Overall survival
- 3) Decreased methylation in candidate genes in the research biopsies as compared to the original resected specimens in patients treated with CC-486.
- 4) Change in quality of life as determined by FACIT-HEp scores

STUDY DESIGN:

This trial is for patients with resected pancreatic adenocarcinoma who have concluded adjuvant therapy or were deemed unable to receive adjuvant therapy with an elevated CA 19-9 or node positive or margin positive disease. CA 19-9 elevation is defined as two levels > the institutional upper limit of normal (ULN) taken at least 2 weeks apart. These levels should be measured after adjuvant therapy has concluded or upon the decision that adjuvant therapy will not be offered. Patients will be randomized to one of two arms. Subjects enrolled due to node + disease or R1 resection must be able to undergo randomization within 3 months of finishing adjuvant therapy or the decision that they are unable to take adjuvant therapy has completed. Group A, the treatment arm, will be started on CC-486. Group B, the control arm, will receive no additional therapy. In both arms, CA 19-9 will be followed and CT scans (or MRI, if clinically indicated) will be done every three months. When patients have visible disease recurrence on imaging, CC-486 will be stopped and both groups will start first-line chemotherapy.

Assuming the maximum accrual with a goal of 2-3 subjects accrued per month, we estimate enrollment duration of 24 months with an additional 12 months for follow-up with concurrent data analysis and manuscript preparation.

TOTAL SAMPLE SIZE:

Maximum 60 patients, with 30 patients in each of the two arms.

[figure not shown]
DRUG SUPPLIES:

For study participants, Celgene Corporation will provide CC-486

DOSING REGIMEN:

Treatment Arm	DRUG	DOSE	FREQUENCY	# of CYCLES	Route
Α	CC-486	300 mg total, three 100 mg tablets	Daily, Days 1- 21, Q28 Day cycles	12 cycles and then follow-up	Oral
В	Observation	N/A	N/A	12 cycles. Follow-up 1 will be collected 3 months after Cycle 10.	N/A

1.2 Schema

2 Schedule of Study Assessments

2.1 Schedule during Initial Phase – Arm A & Arm B

For Arm $A \pm 3$ day window for study assessments and ± 2 weeks for Tumor Assessments. For Arm B, schedule variations are permitted for Tumor Assessments and CA19-9 collection

	Screening	Сус	le 1			cles 4, and 10	Safety Assessment	Upon Visible Disease Progression
Procedure	≤28 days prior to C1D1	(Da	y 1)	(Day 1)	(Day 1)		28 days post d/c CC-486	
		Arm A	Arm B	Arm A	Arm A	Arm B	Arm A	Arm A & B
CC-486 dosing (D1- 21) ²⁰		х		x	х			
Prior medications & anti-cancer Therapies	X							
Physical examination	Х	X ¹		х	Х		Х	X ⁷
Vital signs	Х	X ¹		Х	Х		Х	X ⁷
Weight	Х	X ¹		Х	Х		Х	X ⁷
ECOG performance status ⁹	x	X ¹		х	х		х	X ⁷
Tumor assessment								
including CT or MRI chest/abd/pelvis ¹⁰	Х				X ¹¹	X ^{6, 11, 15}		X ⁷
CBC with differential	Х	X ¹		Х	Х		Х	X ⁷

SKCCC J12138 IND 117362

Confidential									
	Screening	Сус	le 1	Cycles 2, 3, 5, 6, 8, 9, 11 and 12	Cycles 4, 7 and 10		Safety Assessment	Upon Visible Disease	
Procedure	≤28 days prior to C1D1			Day 1)	28 days post d/c CC-486	Progression			
		Arm A	Arm B	Arm A	Arm A	Arm B	Arm A	Arm A & B	
Serum chemistry and hepatic panel	х	X ¹		х	х		х	X ⁷	
PT/PTT	Х							X ⁷	
CA 19-9	Х	X ¹	X ^{1, 6}		Х	X ^{6, 18}		X ⁷	
Pregnancy Test ¹²	Х	X ¹							
Blood collection for correlative studies ¹⁹	x	X ^{1, 3}	X ^{1, 2, 4}	X ³	X ³	X ^{2, 4}		X ⁸	
Tumor biopsy ^{13, 19}								Х	
Record adverse events/symptoms ¹⁷	х	X ¹		Х	х		Х	Х	
Collect remaining pills and diary ²¹				х	х		Х	Х	
Record concomitant therapies/procedures	х	X ¹		х	х		Х	Х	
Archival Tissue ^{16, 19}	Х								
Quality of Life	Х	X ¹	X ^{1, 5}		Х	X ⁵	X ¹⁴	X ⁷	

In order to minimize the need for research-only in-person visits, telemedicine visits may be substituted for in person clinical trial visits or portions of clinical trial visits where determined to be appropriate and where determined by the investigator not to increase the participants risks. Prior to initiating telemedicine for study visits the study team will explain to the participant, what a telemedicine visit entails and confirm that the study participant is in agreement and able to proceed with this method. Telemedicine acknowledgement will be obtained in accordance with the Guidance for Use of Telemedicine in Research. In the event telemedicine is not deemed feasible, the study visit will proceed as an in-person visit. Telemedicine visits will be conducted using HIPAA compliant method approved by the Health System and within licensing restrictions.

- ¹ If study assessment assessed within 7 days of Cycle 1, Day 1, they do not need to be repeated.
- ² Correlative blood sampling is optional for patients in Arm B except for at screening and at time of visible disease progression.
- ³ For patients assigned to Arm A, research blood will be collected for tumor methylation analysis and other correlative studies on Day 1 of *every* cycle.
- ⁴ For patients assigned to Arm B, research blood will be collected for tumor methylation analysis and other correlative studies at screening and/or Cycle 1 Day 1 and Day 1 of *every third* cycle beginning with Cycle 4 (Cycle 4, 7, 10).
- ⁵ Patients on Arm B can provide this information to study team member over the phone.
- ⁶ Patients on Arm B who opt not to participate in correlative blood sampling may be assessed by their local oncologist for all clinical, laboratory and imaging parameters.
- ⁷ If study assessment was completed within 7 days of noting visible disease progression, they do not need to be repeated.
- ⁸ For Arm A patients, if research blood was collected within one month, it does not need to be repeated. For Arm B patients, if research blood was collected within 3 months, it does not need to be repeated.
- ⁹ Please refer to Appendix A for definition of ECOG performance status.
- ¹⁰ Radiologic imaging of chest/abdomen/pelvis (CT preferred, abdominal/pelvis MRI will be performed for patients with CT contrast allergy) and any other imaging required per RECIST for the particular subject are required at baseline must be obtained within 4 weeks of initiation of therapy.
- ¹¹ Assessment for presence of visible disease will occur prior to every third cycle, beginning with Cycle 4 (Cycles 4, 7, 10). For each individual patient, the same imaging modality should be used at assessment as was used during screening.
- ¹² Obtain a urine or serum pregnancy test at screening no more than 7 days prior to dosing on Day 1.
- ¹³ Tumor biopsies will be obtained at the time of visible disease recurrence for all subjects. Location of biopsy can be primary tumor or site of metastatic disease, as determined by the treating oncologist. Tumor biopsy may be obtained within 4 weeks of visible disease progression or before first dose of chemotherapy, whichever occurs latest.
- ¹⁴ Completed only if FACIT data not collected at time of visible disease progression

- ¹⁵ Tumor assessments should ideally be performed within a +/- 2 week window every 3 months (Cycle, 4, 7, and 10). However, Tumor assessment may be completed at the patient's oncologist's discretion outside of the ideal window
- ¹⁶ May be obtained any time throughout the study for both Arm A and Arm B patients.
- ¹⁷ Assessment not required for Arm B patients
- ¹⁸ For Arm B patients CA19-9 may be collected outside of the recommended 3 month window at the patient's local oncologist's discretion.
- ¹⁹ Research samples will be collected at the discretion of the PI based on availability of supplies and safety of patient and staff.
- ²⁰ CC-486 dosing (D1-21) research drug may be shipped to patients to limit contact due to COVID-19 precautions. See Section 5.2.9.1 for more details.
- Review of remaining pills and pill diary may be reviewed during a telemedicine visit when drug is unable to be returned to study staff due to COVID-19 precautions. Copies of the pill diary may be submitted to study staff by phone, email, fax, or mychart.

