5.3.2.2 Arm A for first 12 cycles

Arm A patients will be evaluated on Day 1 of every cycle with a physical examination, ECOG performance status, vital signs, weight, CBC with differential, research blood and serum chemistry and hepatic panel. Arm A patients will also complete an assessment of adverse events and reporting of current medications/procedures on Day 1 of every cycle.

Arm A patients will complete a CA 19-9, quality of life assessment and CT scan on Day 1 of every third cycle beginning at Cycle 4.

Arm A subjects will be evaluated for adverse events on Day 1 of each cycle with the NCI CTCAE v4.0 (http://ctep.info.nih.gov) used as a guide for the grading of severity. For Arm A patients, doses will be reduced for hematologic and other non-hematologic toxicities that can be attributed to the study drug. Dose adjustments are to be made according to the system showing the greatest degree of toxicity. When a dose reduction is required for Day 1 of any cycle, no dose re-escalation will be permitted for the duration of study treatment.

NOTE: Arm B patients will not be evaluated for adverse events as they do not receive the study agent.

Criteria to Initiate Treatment

In Arm A, a new course of treatment may begin on the scheduled Day 1 of a new cycle if:

- Absolute neutrophil count $\geq 1500/\text{mm}^3$
- Platelet count $\geq 100,000/\text{mm}^3$
- Serum creatinine levels < 2 mg/dL
- Serum bilirubin levels $\leq 1.5 \text{ mg/dL}$.
- AST (SGOT) and ALT (SGPT) \leq 2.5 x the institutional upper limit (ULN) of the normal range
- Any other drug-related adverse events that may have occurred must have resolved to < Grade 2 severity except grade 2 anorexia and any correctable metabolic abnormality.
- No evidence of visible disease recurrence on imaging (if indicated per Study Schedule, Section 2, to be done prior to cycles 4, 7, and 10)

If these conditions are not met on Day 1 of a new cycle, the subject will be evaluated weekly and a new cycle of treatment will not be initiated until the toxicity has resolved as described above utilizing the dose modifications as depicted below. If the study drug has to be held for > 28 days, study treatment will be discontinued.

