5.3.2.3 Arm B for the first 12 cycles

Arm B patients will ideally be evaluated (or at the very least contacted by the study team) on Day 1 of every third cycle beginning with Cycle 4.

Patients are permitted to see their local oncologist, and CA19-9 and lesion assessments may be completed outside of the recommended 3 month window (Cycles 4, 7, and 10) at their oncologist's discretion.

Arm B patients will follow a similar schedule as patients in Follow-up, except for a Quality of Life assessment that will be performed.

Correlative blood draw is optional for Arm B patients. If Arm B patients wish, they may have research bloods drawn for correlative studies.

Arm B patients who opt to have research blood collected will have it collected on Day 1 of every third cycle (cycle 4, 7 and 10).

Below is the list of information that must be obtained from Arm B patients.

- Any further therapy received (records to be obtained)
- Subjective response on therapy (records to be obtained)
- Any CA 19-9 drawn (records to be obtained)
- Any imaging (images to be obtained)

Arm B patients will complete a CA 19-9, quality of life assessment and CT scan (or alternate imaging, if clinically indicated) quarterly (ideally).

Arm B patients who are not evaluated in person may have the Quality of Life assessment completed over the [contact] Dose Modification

Table 5.3.1: Arm A: Dose Modification Recommendations for CC-486 Phase
--

Toxicity	Grade	CC-486
Febrile Neutropenia	Grade 3 or 4	Hold until resolved and neutrophils \geq 1500/mm ³
		Restart study drug at 200 mg (two tablets, 33% dose reduction).
		If the same Grade 3 or 4 event recurs (i.e., third occurrence) despite CC-486 dose reduction to 200 mg, as described above, permanently discontinue study
Leukopenia and/or Neutropenia	Grade 2-3Hold dose until recovery to Grade ≤ 1 or baseline.Resume study drug at prior dose	
	Grade 4	Hold until resolved to \leq Grade 1
		Restart study drug at 200 mg (two tablets, 33% dose reduction).
		If the same Grade 4 event recurs (i.e., third occurrence) despite CC-486 dose reduction to 200 mg, as described above, permanently discontinue study drug.
Thrombocytopenia	Grade 1* or 2	Hold treatment until resolution to normal values.
	Grade 3 or 4	Hold until resolved and platelet count ≥100,000/mm ³ Restart study drug at 200 mg (two tablets, 33% dose reduction)
Diarrhea (unresponsive to maximum medical	Grade 1 or 2	Consider administering symptomatic remedies and/or start prophylaxis.

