5.3.2.5 Arm A: Missing doses

Missed Doses Day 1 dose

As Day 1 dose of CC-486 will be given in the office, this dose should not be missed. If the patient does not meet the criteria to begin a new cycle, then the patient will be reassessed in a week and Cycle X Day 1 will start when the dose is actually given.

Day X dose missed

If the dose held or missed was to be given on any day other than Day 1, the cycle continues per protocol with one dose not given and that dose is just considered omitted.

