11.3.3 Quality of life analysis

Quality of life will be assessed at screening and/or cycle 1 day 1 and then every 3 cycles thereafter (cycles 4, 7 and 10) using the Functional Assessment of Chronic Illness Therapy Hepatobiliary Cancer (FACIT-Hep) questionnaire. The hepatobiliary, general function, and subscale scores will

be will be graded according to the guidelines provided at http://www.facit.org. Summary statistics (e.g. means, medians, ranges) and graphical techniques (e.g. box-plots over time) will be used to summarize the patterns of scores over time and assess whether or not transformations are necessary. Comparisons of the differences in the change in scores over time between treatment groups will be performed using generalize estimating equations (GEE). Sensitivity analyses will be performed to assess the impact of missing data including best and worst case single imputation, multiple imputation. One issue when assessing quality of life is how to handle scores for individuals who have died. Some questionnaires (e.g. Stroke modified Rankin Score) include death as a value on the scale; however, this is not the case for the FACIT questionnaires. We will assess the impact of missing data due to death by assessing the worst category score for those who have died.

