Appendix D: FACT – Hep (Version 4)

FACT-Hep (Version 4)

Below is a list of statements that other people with your illness have said are important. Please circle or mark one number per line to indicate your response as it applies to the past 7 days.

	PHYSICAL WELL-BEING	Not at all	A little bit	Some- what	Quite a bit	Very much
arı	I have a lack of energy	0	1	2	3	4
a92	I have nausea	0	1	2	3	4
ars	Because of my physical condition, I have trouble meeting the needs of my family	0	1	2	3	4
GP4	I have pain	0	1	2	3	4
cers :	I am bothered by side effects of treatment	0	1	2	3	4
CP6	I feel ill	0	1	2	3	4
GP7	I am forced to spend time in bed	0	1	2	3	4
	SOCIAL/FAMILY WELL-BEING	Not at all	A little bit	Some- what	Quite a bit	Very much
ası	I feel close to my friends	0	1	2	3	4
CB2	I get emotional support from my family	0	1	2	3	4
GS 3	I get support from my friends	0	1	2	3	4
GS4	My family has accepted my illness	0	1	2	3	4
GS 5	I am satisfied with family communication about my illness.	0	1	2	3	4
CB5	I feel close to my partner (or the person who is my main support)	0	1	2	3	4
QI	Regardless of your current level of sexual activity, please answer the following question. If you prefer not to answer it, please mark this box and go to the next section.					
GS 7	I am satisfied with my sex life	. 0	1	2	3	4

English (Universal) Copyright 1987, 1997 16 November 2007 Page 1 of 3

FACT-Hep (Version 4)

Please circle or mark one number per line to indicate your response as it applies to the past 7 days.

	EMOTIONAL WELL-BEING	Not at all	A little bit	Some- what	Quite a bit	Very much
CE1	I feel sad	0	1	2	3	4
082	I am satisfied with how I am coping with my illness	0	1	2	3	4
083	I am losing hope in the fight against my illness	0	1	2	3	4
CE4	I feel nervous	0	1	2	3	4
085	I worry about dying	0	1	2	3	4
085	I worry that my condition will get worse	0	1	2	3	4

	FUNCTIONAL WELL-BEING	Not at all	A little bit	Some- what	Quite a bit	Very much
arı	I am able to work (include work at home)	0	1	2	3	4
a12	My work (include work at home) is fulfilling	0	1	2	3	4
ars	I am able to enjoy life	0	1	2	3	4
G#4	I have accepted my illness	0	1	2	3	4
ars	I am sleeping well	0	1	2	3	4
aps.	I am enjoying the things I usually do for fun	0	1	2	3	4
97	I am content with the quality of my life right now	0	1	2	3	4

English (Universal) Copyright 1987, 1997 16 November 2007 Page 2 of 3

FACT-Hep (Version 4)

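### Only Arm B has a stated phone option for the quality-of-life form, and the plan neither records mode of completion nor examines it when comparing change between arms

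*Combined protocol and SAP*

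**What the plan says.** **Arm B.** In the Section 2.1 schedule, the Quality of Life cells for Arm B at Cycle 1 and at Cycles 4, 7 and 10 carry footnote 5: "Patients on Arm B can provide this information to study team member over the phone". The Arm A, screening and progression cells do not carry it. Section 5.3.2.3 has the matching provision, "Arm B patients who are not evaluated in person may have the Quality of Life assessment completed over the" (the public copy breaks off there), and asks at minimum for contact by the study team. Section 5.1 lets observation patients who cannot travel be followed by a local oncologist.

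**Arm A.** Section 5.3.2.2 gives the timing: "Arm A patients will complete a CA 19-9, quality of life assessment and CT scan on Day 1 of every third cycle", starting at Cycle 4. It names no mode. The setting follows from Section 5.3.2.5: "As Day 1 dose of CC-486 will be given in the office, this dose should not be missed". Section 5.2.9.1 likewise places the Day 1 dose in clinic.

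**Either arm.** Below the schedule table, Section 2.1 says "telemedicine visits may be substituted for in person clinical trial visits or portions of clinical trial visits where determined to be appropriate". No arm is named.

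**Instrument.** Appendix D reproduces a written form: "Please circle or mark one number per line to indicate your response".

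**Analysis.** Section 11.3.3 states: "Quality of life will be assessed at screening and/or cycle 1 day 1 and then every 3 cycles thereafter". It compares change in scores between arms by GEE. Its sensitivity analyses deal with missing data and death. Neither that section nor the schedule mentions mode of completion.

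**The concern.** A change score is easiest to interpret when both measurements were taken the same way. Marking a form oneself and speaking answers to a member of the study team are different ways of taking the measurement, and the form covers private matters such as sadness, fear of dying and sex life. If the two modes give different average answers, and one arm uses the phone more than the other, part of the between-arm difference in change reflects mode and not CC-486.

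The schedule makes that pattern possible. Screening includes an examination and laboratory tests in both arms, so the first form is normally completed in person. At Cycles 4, 7 and 10, Arm A has an examination, bloods and a supervised dose on the day. Arm B has no examination or safety bloods scheduled, and may be followed elsewhere and reached by phone.

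At stake is the reading of secondary endpoint 4, change in quality of life (Section 4.2). If mode is not noted when the form is completed, it may not be recoverable at analysis.

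**Working it through.** **No figure to reproduce.** The documents give no quality-of-life effect size, SD, power or sample size. The check sets the provisions side by side and then illustrates the possible size.

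**Provisions by arm**

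| Time point | Arm A | Arm B |
|---|---|---|
| Screening | In person by default; no phone footnote | Same |
| Cycle 1 Day 1 | Office by default | Phone allowed |
| Cycles 4, 7, 10 | Office by default | Phone allowed |
| Progression | No phone footnote | No phone footnote |
| Telemedicine | Allowed | Allowed |

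Section 11.3.3 sets baseline at screening and/or Cycle 1 Day 1. An Arm B patient with a screening form and later phone forms changes mode after baseline. One whose baseline is a Cycle 1 phone form need not.

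**Inputs for the illustration**
- n = 30 per arm: Section 1.1, total sample size.
- Two-sided 5% level: Section 11.3.1 gives p < 0.05 for the efficacy analyses. Two-sidedness and its use for quality of life are assumptions.
- Mode shift m, in SDs of the change score: assumed, 0.1 to 0.5.
- Share f of Arm B follow-up forms by phone: assumed, 25% to 100%.
- Share g of Arm A forms completed remotely with the same shift: assumed 0 unless stated.
- Baseline in person in both arms; no true difference.

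**Formulas**
- Bias = (f − g) × m.
- SE = √(2/n) = √(2/30) = 0.258 SD.
- Rejection probability = P(|Z + bias/SE| > 1.96).

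**Worked cases, m = 0.3 and g = 0**
- f = 1: bias 0.30 SD; 0.30/0.258 = 1.16; rejection 21.3%.
- f = 0.5: bias 0.15 SD; 0.15/0.258 = 0.58; rejection 9.0%.

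**Rejection rate against a nominal 5%, n = 30 per arm, g = 0**

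| Arm B share by phone | m = 0.1 | m = 0.2 | m = 0.3 | m = 0.5 |
|---|---|---|---|---|
| 25% | 5.1% | 5.4% | 6.0% | 7.7% |
| 50% | 5.4% | 6.7% | 9.0% | 16.2% |
| 75% | 6.0% | 9.0% | 14.1% | 30.6% |
| 100% | 6.7% | 12.1% | 21.3% | 49.1% |

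Bias falls in proportion to phone use; the rejection rate does not. At 0.3 SD, halving the phone share halves the bias but cuts the excess over 5% from 16.3 to 4.0 points, about a quarter.

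**Effect of telemedicine in Arm A.** With f = 0.75 and m = 0.3, bias is 0.225 SD if g = 0, (0.75 − 0.25) × 0.3 = 0.15 SD if g = 0.25, and (0.75 − 0.50) × 0.3 = 0.075 SD if g = 0.50.

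**Fewer evaluable patients.** With 20 per arm, f = 0.75, m = 0.3 and g = 0, rejection is 11.0%.

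This is a single-time-point normal approximation. The planned GEE uses repeated measures, so the figures indicate scale only.

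**The case against.** The strongest reply is that the documents do not show the arms being measured differently. No section says where or how Arm A completes the form; office completion is inferred from where the Day 1 dose is given. Telemedicine is open to Arm A, and Sections 5.2.9.1 and 5.2.10 describe shipped drug and remote pill review for that arm. The Arm B phone option is permissive, so its uptake may be small. All of this stands. A reader might infer that a mode change is confined to Arm B, or that mode and treatment are bound to be confounded. The text supports neither.

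Three further points stand:
- Objective 5 in Section 4.1 is to evaluate quality of life on CC-486 and names no comparison. The comparison between arms enters through Section 11.3.3.
- The documents contain nothing on whether, or in which direction, phone answers differ from marked ones. Staff knowledge of allocation does not distinguish the arms either, since the trial compares a drug with untreated observation.
- The phone option has a purpose. Arm B patients may not attend the study site, and replacing phone outright with posted forms could increase missing forms in that arm.

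What the reply does not remove is that the explicit phone provision belongs to one arm and that mode is neither recorded nor examined. Telemedicine could narrow the imbalance or add further variation; without a record, nobody could tell which.

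**Conclusion.** The point holds as a risk, not as a demonstrated bias. Mode of completion may differ by arm and may change after baseline within Arm B, and the planned comparison of change has no means of detecting either. Size and direction are unknown. The 21% and 9% rejection rates at a 0.3 SD shift rest on assumed values for the shift and the phone share, in-person baselines, and no remote completion in Arm A. With small shifts or little phone use, the rate stays close to 5%.

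The scope is one secondary endpoint for which no power is stated. PFS and OS are unaffected. This is a cheap improvement worth making, not a flaw in the main design.

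**What to change.** - **Section 2.1 footnote 5 and Section 5.3.2.3:** reword so that the same modes are open to both arms. Prefer self-completion, in clinic or by portal, email or post, and keep phone as a fallback in either arm to limit missing forms. Keep mode constant within a patient where possible.
- **CRF:** add one field for mode at every quality-of-life assessment, including baseline.
- **Section 11.3.3:** add a sensitivity analysis restricted to self-completed forms, or to patients whose baseline and follow-up forms used the same mode, and tabulate mode by arm and visit.

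A mode covariate alone is not enough: if mode largely coincides with arm, the model cannot separate them. Aligning the modes comes first.

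The cost is some rewording, one data field and some reminders. Some remote forms may come back late or not at all, which the phone fallback limits. Section 5.2.10 already accepts pill diaries by email, fax or portal, so similar return routes are in use.
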